Statistical Methods:	
Populations for Analysis
 
Patients will be categorized into the following populations for analysis:
 
 • FAS: The FAS consists of all patients enrolled in the run-in phase who either completed at least 3 cycles of study treatment or experience a DLT, and all patients enrolled in the continuation phase (Phase II). • Per-protocol (PP) population: The PP population will consist of all patients who completed at least 3 cycles of study treatment regimen defined for Phase II, have measurable baseline disease and, at least, one post-baseline RECIST assessment (PD, SD, PR or CR). Patients with a major protocol deviation or AE, deemed by the Medical Monitor to have an impact on the study endpoints, will be excluded from the PP population. • Safety population: The safety population will consist of all patients who received, at least, one dose of SCB01A, and have at least one post-dose safety evaluation. • PK population: The PK population will consist of all patients who received, at least, one dose of SCB01A with sufficient post-dose bio-samples collected for PK profile characterization (run-in phase

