	
only).
 
Details of any other populations for analysis will be described in the statistical analysis plan (SAP).
 
Statistical Analysis
 
Assumption of sample size calculation:
 
• Study design: Simon's optimal two stage design^{1,2}• Type I error (one-sided): 10%• Power: 80%• Response probability of null hypothesis (P0): 0.10• Response probability of SCB01A (P1): 0.25 
According to these hypotheses, up to 64 patients need to be recruited into the study (including patients from the run-in phase). At least 6 patients are required to achieve CR, PR or SD at the end of the 9th week after first treatment with SCB01A for the study to meet its primary objective. The trial will be discontinued if DC is observed in one or none patients after the Stage 1 Disease Controls Review.
 
Stopping rule: stopped early for futility if less than 2/13 (including 0 or 1 of 13 patients) show DCR in Stage 1 of Phase II with no further investigation of the drug if less than 6/34 achieve DCR by the end of Stage 2 of Phase II.
 
Both according to FAS and PP approaches (all enrolled patients who meet the eligibility criteria and do not present major deviations during the study) will be included in the analyses. The conclusion will be summarized according to analyses of PP population. Inferential analysis results will be expressed as point estimates and their 95% confidence intervals (CIs). To be consistent with the sample size calculation, the 90% CI will also be presented. Analyses will be carried out using SAS® Software, version 9.3 or higher (SAS Institute, Cary, North Carolina, USA).
 
All time-to-event endpoints, including OS time and PFS, will be reported in days (median with 95% CI and range) and calculated using Kaplan-Meier methods. Patients who have not progressed or who have died at the time of the analysis will be censored at the last disease assessment date.
 
PK Evaluations
 
The blood samples will be assayed for SCB01A and PK parameters (area under the plasma concentration-time curve from time zero to time t [AUC_{0-t}], area under the plasma concentration-time curve from time zero to infinite time [$AUC_{0-\infty}$], and maximum plasma concentration [C_{max}], clearance [CL], volume of distribution [V_d], half-life [$t_{1/2}$], elimination

--	--

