8.3. Populations for Analysis

Patients will be categorized into the following populations for analysis:

FAS: The FAS consists of all patients enrolled in the run-in phase who either completed at least 3 cycles of study treatment or experience a DLT, and all patients enrolled in the continuation phase (Phase II).

Per-protocol (PP) population: The PP population will consist of all patients who completed at least 3 cycles of study treatment regimen defined for Phase II, have measurable baseline disease and at least one post-baseline RECIST assessment (PD, SD, PR or CR). Patients with a major protocol violation, or AE, deemed by the Medical Monitor to have an impact on the study endpoints will be excluded from the PP population.

Safety population: The safety population will consist of all patients who received at least one dose of SCB01A, and have at least one post-dose safety evaluation.

PK population: The PK population will consist of all patients who received at least one dose of SCB01A with sufficient post-dose bio-samples collected for PK profile characterization.

Details of any other populations for analysis will be described in the SAP.

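### The protocol rests the Phase II conclusion on a per-protocol set from which the Medical Monitor may remove patients for an adverse event, and it describes that set in two ways

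*Protocol*

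**What the plan says.** The protocol describes the PP population in three places.

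- **Synopsis, Populations for Analysis.** "The PP population will consist of all patients who completed at least 3 cycles of study treatment regimen defined for Phase II", with measurable baseline disease and at least one post-baseline RECIST assessment. It then adds: "Patients with a major protocol deviation or AE, deemed by the Medical Monitor to have an impact on the study endpoints, will be excluded".
- **Section 8.3.** The same conditions, and the same exclusion with one word changed: "Patients with a major protocol violation, or AE, deemed by the Medical Monitor to have an impact on the study endpoints will be excluded".
- **Synopsis, Statistical Analysis.** A parenthesis describes the approach as "all enrolled patients who meet the eligibility criteria and do not present major deviations during the study". It mentions no AE, Medical Monitor, number of cycles, measurable disease or RECIST assessment.

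The last of these places then states: "The conclusion will be summarized according to analyses of PP population". It also says that FAS and PP analyses will both be done. Section 8.5 names no population for the conclusion.

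Success is stated as at least 6 patients with disease control at Week 9 (synopsis and Section 8.2), also written as 6/34 in the synopsis stopping rule and Section 8.8. Phase II patients are not replaced. Section 4.10 confirms that the study is open-label.

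The SAP was written after the study stopped in the run-in phase with five patients enrolled. Its Section 4 keeps only the FAS, Safety and PK populations, and its Section 10 analyses efficacy on the FAS.

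**The concern.** A protocol deviation is a departure from the plan. An AE on study drug is something that the treatment may have caused. Taking a patient out of the denominator because of an AE conditions the efficacy estimate on an outcome of treatment. The criterion is whether the AE affected the study endpoints, so the judgement is tied to the result being estimated. The protocol does not say which AEs qualify or when the decision must be made, and there is no blinding or control arm to limit its effect.

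The clause also reaches patients whom the other PP conditions keep in: those who completed 3 cycles and were scanned. Under the population list and Section 8.3 such a patient can be removed. Under the Statistical Analysis description the same patient stays if eligible and free of major deviations. One dataset can thus give two PP estimates of DCR, and PP is the set on which the synopsis bases its conclusion.

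**Working it through.** **1. Inputs (synopsis, Statistical Analysis).** "Study design: Simon's optimal two stage design"; "Response probability of null hypothesis (P0): 0.10"; alternative 0.25; one-sided type I error 10%; power 80%. Stop if 0 or 1 of 13 are controlled in stage 1; success needs at least 6 of 34. SAP Section 2.1 gives the same boundaries. (Sections 3.1, 8.2, 8.5 and 8.8 of the protocol state a different stage 1 boundary, which is a separate matter.)

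**2. Reproducing the design.** With 13 patients in stage 1 and 21 in stage 2,

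P(success) = sum over x = 2 to 13 of P[Bin(13, p) = x] × P[Bin(21, p) ≥ 6 − x].

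At p = 0.10 this is 0.0957; at p = 0.25 it is 0.811. A search for the smallest expected sample size under the null returns the same design. The stated figures are right, and they hold for all 34 patients counted.

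**3. Removing non-controlled patients.** The documents give no rate of AE exclusion, so the number removed, k, is an assumption, shown for 4 to 7. Every removed patient is taken as non-controlled, which moves the estimate upward the most. The count of controlled patients stays at 6 and the denominator is 34 − k. The 90% Clopper-Pearson limits (the exact method named in SAP Section 10.1) are the 5% quantile of Beta(x, n − x + 1) and the 95% quantile of Beta(x + 1, n − x).

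| k | x/n | DCR | 90% CI |
|---|---|---|---|
| 0 | 6/34 | 17.6% | 8.0-31.9% |
| 4 | 6/30 | 20.0% | 9.1-35.7% |
| 5 | 6/29 | 20.7% | 9.4-36.8% |
| 6 | 6/28 | 21.4% | 9.8-38.0% |
| 7 | 6/27 | 22.2% | 10.1-39.2% |

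The decision is success in every row, because 6 are controlled. The estimate and interval rise. The lower limit exceeds the 10% null only at k = 7.

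**4. Removing a controlled patient.** If exactly 6 are controlled and one of them is excluded for an AE, the PP count is 6 − 1 = 5. That is below 6, and the decision reverses.

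**5. The completion condition.** A patient who stops before 3 cycles because of toxicity already fails the PP definition in the population list and Section 8.3. Deleting the AE ground alone would not return that patient to the denominator.

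**The case against.** Four points can be made in the plan's defence.

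- **The two formal definitions agree.** The population list and Section 8.3 both contain the AE ground. The differing text is a loose parenthesis placed after a mention of both FAS and PP. This stands in part. However, the parenthesis does not fit the FAS, which has no deviation condition, so it reads as a description of PP. It also drops the 3-cycle, measurable-disease and RECIST conditions, so the mismatch is wider than the AE clause.
- **The FAS is analysed too.** It keeps every Phase II patient, so a difference between FAS and PP would be visible. This stands as a safeguard, but the synopsis still draws the conclusion from PP.
- **The Medical Monitor is called independent** in the synopsis's description of the safety committee, and SAP Section 6 has deviations categorised before database lock. The SAP step covers deviations and not AEs. A reader might infer that the monitor decides with the tumour result in view. The documents do not say so; they only fail to prevent it.
- **The SAP has no PP population.** This stands in full. No analysis still to be run uses the clause.

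A reader might also infer that excluding non-controlled patients could turn a failed trial into a success. That would need the boundary to be read as a proportion: 5/34 = 14.7% misses 6/34 = 17.6%, while 5/28 = 17.9% would pass. The synopsis and Section 8.2 require a number of patients, at least 6, so the documents do not support that reading. Nor do they make a confidence limit above 10% the test of success.

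**Conclusion.** The point holds for the protocol's planned Phase II analysis. The set that carries the conclusion allows discretionary removal for a treatment outcome, without criteria or timing, and it is described inconsistently.

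The effect is limited. Removal of non-controlled patients inflates the reported DCR by 2.4 percentage points with 4 exclusions (20.0 − 17.6) and by 4.6 with 7 (22.2 − 17.6), without changing the decision. Both numbers of exclusions are assumed, with every excluded patient non-controlled. Seven is a demanding assumption, since the clause adds only patients who meet the other PP conditions. A reversed decision requires removal of a controlled patient when exactly 6 are controlled.

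A reader might infer that the trial's reported efficacy results are affected. They are not: Phase II recruited nobody and the SAP uses the FAS. The defect would matter if this protocol text were reused.

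**What to change.** 1. Delete the AE ground from the exclusion sentence in the synopsis population list and in Section 8.3, so that only protocol deviations exclude.
2. Replace the parenthesis under Statistical Analysis with a reference to that single PP definition.
3. Fix and date the list of excluding deviations before Week 9 responses are summarised.
4. Base the 6-of-34 conclusion on the FAS, with PP as supportive. Count all Phase II patients, and score those without a Week 9 assessment as not controlled. This step is needed because the 3-cycle condition in PP would still remove patients who stop early for toxicity. The 34 also includes run-in patients treated at the Optimal Dose (Section 3.1), so state that the FAS is restricted to that dose for this test. Align the DCR evaluability sentence in the synopsis and Section 8.5, which requires an on-study disease assessment.

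The cost is wording in the synopsis and in Sections 8.3 and 8.5, plus one dated list. The downside is that the DCR that carries the conclusion may be slightly lower. The design then keeps the denominator for which its 0.0957 and 0.811 were calculated.

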1. Known primary CNS malignancy or CNS involvement (except for brain metastases that have been treated and are stable and patient is off steroids);
2. Systemic cancer therapy, Chemotherapy, radiation therapy, major surgery or investigational agents less than 4 weeks prior to study drug treatment;
3. History of malignancy other than head and neck cancer. Second primary head and neck tumors are excluded with the exception of early stage non-melanoma skin cancer or carcinoma *in situ* of cervix;
4. Ultrasound or radiological evidence of liver cirrhosis;
5. Severe pulmonary obstructive or restrictive disease;
6. Uncontrolled inflammatory disease (autoimmune or infectious);
7. Clinically significant cardiac disease (NYHA class > 2);
8. Other serious illness or medial conditions, such as active infection, unresolved bowel obstruction, or psychiatric disorders;
9. Known HIV positivity;
10. Participation in another clinical trial or treatment with any investigational drug within 30 days prior to study entry;
11. QTc $> 450 \text{ msec}$;
12. Pregnant or breast-feeding patients, and men and women of child-bearing potential not using effective contraception while on study treatment; Known hypersensitivity to any component of SCB01A;

	
13. History of exposure to SCB01A or its analogues;
 
14. History of active or significant neurological disorder or psychiatric disorder that would prohibit the understanding and giving of informed consent, or would interfere with the clinical and radiological evaluation of central nervous system during the trial;
 
15. Any other reason the investigator deems the patient to be unsuitable for the study

Duration of Treatment:	Patients will receive the recommended dose of monotherapy of SCB01A for 9 weeks (3wk*3 cycles) or until disease progression, intolerable toxicity, consent withdrawal or death, whichever occurs first.

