Endpoints:	
Primary endpoint:
 
 DCR, defined as; complete response (CR) + partial response (PR) + stable disease (SD) at Week 9, according to RECIST v1.1 criteria 
Secondary endpoints:
 
 PFS OS rate at 36 weeks after first treatment with SCB01A Safety: The safety endpoints used to achieve the secondary objectives of this study are: 
 Hematology, clinical chemistry, coagulation factors and urinalysis laboratory data changes AE/SAE incidence Physical examination results changes Vital sign changes Electrocardiogram (ECG) (including PR, QRS, QT, QTc, and RR intervals) results Health outcomes assessment using patient-reported EORTC QLQ-C30 and H&N35 questionnaires.
Criteria for Evaluation:	
Efficacy measurements:
 
Tumor Measurement:
 
Tumor response will be assessed by using computerized tomography (CT) or MRI scans according to RECIST v1.1 at baseline, and every 3 cycles prior to the next cycle until progression of the disease. For patients who meet DC criteria after the first 3 cycles of study treatment, additional radiological tumor assessments will be performed at Week 12. Scans must include brain, chest, abdomen, and pelvis. The imaging technique used at baseline should be used throughout the study.
 
Patients will be considered evaluable for DCR in this study if they fulfill the criteria for evaluation according to RECIST v1.1, i.e., those patients who undergo a baseline disease assessment within 4 weeks of treatment initiation, and who undergo at least 1 disease assessment on the study.
 
 DCR is defined as the percentage of patients who have achieved CR, PR and SD at a particular time point after first treatment, according

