3.4. End of Treatment (EOT) Evaluation/Early Withdrawal

EOT visit should be conducted 21 ± 2 days after the last infusion. Early withdrawal visit should be conducted within 21 days after the patient receives the last dose of study treatment.

The following assessments will be performed at the EOT/early withdrawal visit:

- Physical examination
- Vital signs
- ECOG performance status
- AEs
- Concomitant medication
- 12-lead ECG
- Tumor assessment (radiological imaging)
- Urinalysis
- Laboratory tests (hematology, clinical chemistry and coagulation)
- EORTC QLQ-C30 and H&N35

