8.5. Efficacy Analysis

The primary efficacy analysis will be performed to assess the DCR and secondary efficacy analysis will be performed to assess the PFS and overall survival rate.

Patients will be considered evaluable for DCR in this study if they fulfill the criteria for evaluation according to RECIST v1.1, i.e., those patients who undergo a baseline disease assessment within 4 weeks of treatment initiation, and who undergo at least 1 disease assessment on-study:

- DCR is defined as the percentage of patients who have achieved CR, PR and SD at a particular time point after first treatment, according to RECIST v1.1.
- PFS is defined as the time from the start of treatment up to the date of first progression based on RECIST v1.1, second primary malignancy or death from any cause, whichever occurs first.
- Overall survival rate is defined as the percentage of patients who are still alive at 36 weeks after first treatment with SCB01A.

Inferential analysis results will be expressed as point estimates and their 95% CIs. To be consistent with the sample size calculation, the 90% CI will also be presented for the primary endpoint. Analyses will be carried out using SAS® Software, version 9.3 or higher (SAS Institute, Cary, North Carolina, USA).

All time-to-event endpoints, including overall survival time and PFS, will be reported in days (median with 95% CI and range) and calculated using Kaplan-Meier methods. Patients who have not progressed or who have died at the time of the analysis will be censored at the last disease assessment date.

The study will be stopped early for futility if less than three DCRs are observed following the completion of the first stage of Phase II. In addition, no further investigation of the drug will be pursued if less than 6 patients achieve DCR by the end of Stage 2 of Phase II.

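### The Phase II conclusion rests on a per-protocol set that requires three completed cycles, so early progressions and deaths can drop out of the Week 9 disease control rate

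*Protocol*

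**What the plan says.** The synopsis (Statistical Analysis) requires both FAS and PP analyses and then gives PP priority: "The conclusion will be summarized according to analyses of PP population". Section 8.5 does not repeat that sentence, and section 8.3 gives no set priority.

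The protocol describes the patients behind the disease control rate (DCR) in several ways:

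- **PP** (synopsis, Populations for Analysis, and section 8.3): "The PP population will consist of all patients who completed at least 3 cycles of study treatment regimen defined for Phase II", with measurable baseline disease and at least one post-baseline RECIST assessment. The Medical Monitor may also exclude patients for a major deviation or an adverse event.
- **A second description** (synopsis, Statistical Analysis, in parentheses after naming FAS and PP): "all enrolled patients who meet the eligibility criteria and do not present major deviations during the study". It has no three-cycle condition.
- **Evaluable for DCR** (synopsis, Criteria for Evaluation, and section 8.5): a baseline assessment within four weeks of starting treatment, in patients "who undergo at least 1 disease assessment on-study". It has no three-cycle condition either.
- **FAS**: every Phase II patient, plus run-in patients at any dose who completed three cycles or had a DLT.

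The primary endpoint is CR, PR or SD at Week 9. Treatment runs for nine weeks "or until disease progression, intolerable toxicity, consent withdrawal or death, whichever occurs first". The decision rule is a count: stop at 0 or 1 of 13, and require at least 6 of 34. SAP section 2.1 states that count over the 34 subjects enrolled.

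**The concern.** Membership of PP depends on getting through the window in which the endpoint is measured. A patient with clinical progression in cycle 2, or who dies in cycle 3, has not achieved Week 9 disease control but is outside the set that carries the conclusion. The PP rate and its interval are biased upward whenever the excluded patients have less disease control than those retained.

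Two consequences follow. A result that fails 6/34 could be reported with a clearly higher PP rate. And because the DCR population is described in several ways, there is some room to settle the denominator after the data are seen.

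**Working it through.** **1. The plan's own design.** Inputs from the synopsis: P0 = 0.10, P1 = 0.25, one-sided alpha 10%, power 80%, continue with at least 2/13, succeed with at least 6/34. The exact probability of success is the sum over x = 2 to 13 of P(X1 = x) × P(X2 ≥ 6 − x), with X1 ~ Bin(13, p) and X2 ~ Bin(21, p). This gives 0.0957 at p = 0.10 and 0.8108 at p = 0.25. A full search for Simon's optimal design under these inputs returns the same 1/13 and 5/34. The stated design is reproduced. (Sections 3.1, 8.2, 8.5 and 8.8 give a different Stage 1 cut-off; that is a separate issue.)

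**2. Expected PP rate.** Let q be the share stopping before three completed cycles and d the share of those stoppers with disease control. Then PP DCR = (0.10 − q·d)/(1 − q) when the true rate is 10%. The documents give neither q nor d, so both are assumed:

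| d | q = 10% | 20% | 30% | 40% | 50% |
|---|---|---|---|---|---|
| 0 (maximum bias) | 11.1% | 12.5% | 14.3% | 16.7% | 20.0% |
| 5% | 10.6% | 11.3% | 12.1% | 13.3% | 15.0% |
| 10% | 10.0% | 10.0% | 10.0% | 10.0% | 10.0% |
| 15% | 9.4% | 8.8% | 7.9% | 6.7% | 5.0% |

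The 40% and 50% columns are the extreme end.

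**3. Observed counts, with Clopper-Pearson 90% intervals.** Seven of 34 outside PP is 20.6%; fourteen of 34 is 41.2%.

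| Controls in all 34 | Outside PP (controlled among them) | All 34 | PP |
|---|---|---|---|
| 6 | 7 (0) | 17.6% (8.0–31.9) | 6/27 = 22.2% (10.1–39.2) |
| 6 | 7 (1) | 17.6% (8.0–31.9) | 5/27 = 18.5% (7.6–35.1) |
| 6 | 7 (2) | 17.6% (8.0–31.9) | 4/27 = 14.8% (5.2–30.8) |
| 5, fails the rule | 7 (0) | 14.7% (6.0–28.5) | 5/27 = 18.5% (7.6–35.1) |
| 5, fails the rule | 14 (0) | 14.7% (6.0–28.5) | 5/20 = 25.0% (10.4–45.6) |

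In the first row the 90% interval moves from including P0 = 10% to just excluding it. In the last row a failing result is reported at the value of P1.

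**4. Effect on the decision rule.** Counted over all enrolled patients, the rule is not touched by PP exclusions in Phase II. If controls were counted only within PP, with 13 and 34 still the numbers enrolled, the effective rate is p − q·d and the rule becomes conservative. With q = 20% and d = 10%, 0.10 − 0.02 = 0.08 gives type I error 0.040, and 0.25 − 0.02 = 0.23 gives power 0.744. With d = 25%, 0.25 − 0.05 = 0.20 gives power 0.614.

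**5. Run-in patients in the Stage 1 thirteen.** Run-in patients who neither complete three cycles nor have a DLT are replaced. The fixed enrolment of 7 or 10 in the synopsis implies that the replaced patients are left out of the thirteen; the literal wording of protocol section 3.1 and SAP section 2.1 would count them. Only on the first reading does selection reach the type I error. At q = 20% and d = 0, the retained run-in patients have rate 0.10/0.80 = 0.125. Three of these plus ten at 0.10 gives 0.106. With a six-patient cohort, five at 0.125, one DLT patient at 0 or 0.10 and seven at 0.10 gives 0.099 or 0.113. Against 0.096 these are small changes.

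**The case against.** The strongest reply is that the harm is limited. The go/no-go rule is a count, Phase II patients are not replaced, and PP exclusions cannot add disease controls. FAS results will be shown alongside. This stands, and it confines the problem to the reported estimate and interval.

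The bias may also be modest. The first scheduled on-study scan is at the end of cycle 3, so progression first seen there stays in PP as progressive disease. Only earlier clinical progression, unscheduled imaging, toxicity, withdrawal or death removes a patient. At 10–20% early stopping, the largest shift from a true 10% is 1.1 to 2.5 percentage points. Some exclusions work the other way: a patient whose last infusion is on Day 43 (cycle 3, Day 1) has an end-of-treatment visit with imaging due around Day 43 + 21 = 64, the Week 9 time point, and may show stable disease. The Medical Monitor's adverse-event exclusion can also act in either direction. All of this is fair; the direction is likely but not certain.

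It can be said too that PP is named in advance, that the parenthesis is shorthand for PP, and that the evaluability criterion applies within a population. That weakens the charge of a free choice of denominator, but the texts still do not describe the same patients. FAS does not settle it, because as worded it mixes run-in patients from every dose level and is not the 34 of the decision rule.

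Finally, the study stopped in the run-in phase with five enrolled and none in Phase II (SAP section 1), and SAP sections 4 and 10 analyse efficacy on an FAS of all run-in subjects, without PP. There is no consequence for the analysis of this trial. The SAP attributes the change of populations to early termination, so the Phase II plan in the protocol remains as written.

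**Conclusion.** The point holds for the protocol's Phase II plan and should be fixed. The set that carries the conclusion is conditioned on completing the endpoint window, and failures before the end of cycle 3 leave it. On the assumption that no early stopper has disease control, a true 10% is reported as 11.1% to 14.3% for early stopping of 10% to 30%, and six controls at about 20% early stopping read as 22.2% instead of 17.6%. With some control among early stoppers the bias shrinks, vanishes when their rate equals the overall rate, and reverses beyond that. Type I error and power of the rule counted over enrolled patients stay at 0.096 and 0.81, apart from the small run-in effect, which depends on how the thirteen are counted.

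**What to change.** Base the conclusion on all patients dosed at the Optimal Dose: run-in patients at that dose, including those replaced for DLT evaluation, plus all Phase II patients. Count anyone without documented Week 9 disease control as not controlled. State that the Stage 1 and 6/34 cut-offs are counts over this set. Express Stage 1 enrolment as 13 minus the number already dosed at the Optimal Dose, in place of the fixed 7 or 10 in the synopsis. Reconcile the PP definition (synopsis and section 8.3), the parenthetical description (synopsis) and the evaluability criterion (synopsis and section 8.5) into one PP definition, used for sensitivity. Summarise other dose levels separately.

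The cost is protocol wording. The totals of 13 and 34 stay, and new Phase II enrolment is the same or lower. The downside is a possibly less favourable reported DCR. The SAP for the terminated study needs no change on this point.
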